# **15.2** Reporting and Managing Protocol Deviations

The study site principal investigator has the responsibility to identify, document and report protocol deviations as directed by the study Sponsor. However, protocol deviations may also be identified during site monitoring visits or during other forms of study conduct review. Upon determination that a protocol deviation has occurred, the staff will a) notify the Principal Investigator, b) notify the NIAID Project Manager and c) will begin completing the Protocol Deviation CRF. The PI will be responsible for providing NIAID with listings of all protocol deviations periodically. NIAID may request discussion with the Principal Investigator and the Independent Medical Monitor to determine the effect of the protocol deviation on the study.

# **16** Ethical Considerations and Compliance with Good Clinical Practice

### 16.1 Statement of Compliance

This clinical study will be conducted using good clinical practice (GCP), as delineated in *Guidance for Industry: E6 Good Clinical Practice Consolidated Guidance*, and according to the criteria specified in this study protocol. Before study initiation, the protocol and the informed consent documents will be reviewed and approved by the *[select: IRB, Ethics Committee]*. Any amendments to the protocol or to the consent materials will also be approved by the *[select: IRB, Ethics Committee]* before they are implemented.

### 16.2 Informed Consent Process

The consent process will provide information about the study to a prospective participant and will allow adequate time for review and discussion prior to his/her decision. The principal investigator or designee listed on the Investigator of

Record form will review the consent and answer questions. Study staff approved by the Investigator and IRB as qualified may also obtain consent. The prospective participant/parent will be told that being in the trial is voluntary and that he or she may withdraw from the study at any time, for any reason. All participants (or their legally acceptable representative) will read, sign, and date a consent form before undergoing any study procedures. Consent materials will be presented in participants' primary language. A copy of the signed consent form will be given to the participant.

The consent process will be ongoing with verbal review of the nature of the study at least yearly. The consent form will be revised when important new safety information is available, the protocol is amended, and/or new information becomes available that may affect participation in the study.

# 16.3 Privacy and Confidentiality

A participant's privacy and confidentiality will be respected throughout the study. Each participant will be assigned a unique identification number and these numbers rather than names will be used to collect, store, and report participant information. Site personnel will not transmit documents containing personal health identifiers (PHI) to the study sponsor or their representatives.

# **17** Publication Policy

The *NIH* policy on the publication of study results will apply to this trial.

The purpose of this SAP is to outline the planned analyses to be completed for the "ChAllenging to Food with Escalating ThrEsholds for Reducing Food Allergy" (CAFETERIA) trial (protocol number AADCRC-ISMMS-03). The SAP is based on protocol [clinicaltrials.gov ID NCT03907397] revision 3.0 finalized November 2021. This SAP covers study endpoints related to the primary and secondary clinical objectives and does not address the primary and secondary mechanistic objectives. The analyses identified in this SAP will be included in abstracts and manuscripts reporting the results of the trial. Exploratory analyses not necessarily identified in this SAP may also be performed. Any post hoc, or unplanned, analyses not explicitly identified in this SAP will be clearly identified as such in any published papers from this study. This SAP may be updated in response to additional developments, either within or outside the trial. All revisions will be made prior to the data lock and the primary analysis.

1. INTRODUCTION

Food allergy affects up to 5% of adults and 4-8% of young children in the US, an estimated 15 million Americans.^{1,2} Food allergy carries a significant cost, and a negative impact on nutrition and quality of life.³⁻⁶ Peanut allergy affects nearly 2% of children, is often severe, and life-long.⁷ The current standard for food allergy management relies on strict avoidance of the offending food. Children are monitored for resolution of food allergy with periodic oral food challenges (OFC), which are performed when diagnostic tests and the medical history suggest a possibility that the allergy has resolved. An OFC involves gradually feeding increasing amounts of the food under medical supervision until a "meal-sized" portion is ingested, unless there are symptoms requiring cessation of dosing. These tests are performed by allergists for clinical diagnosis when they suspect resolution of peanut allergy or sensitization without reactivity, using office-measured foods such as peanut butter, peanut flour, or Bamba, in amounts measured by common kitchen materials such as spoons.⁸ A child who reacts at any dose during an OFC, even at the top dose, even with mild symptoms, is considered allergic and advised to continue strict avoidance until the next OFC is performed, typically not less than a year later.^{4,9-11}

However, the paradigm of strict avoidance of a food as therapy for food allergy is changing. We believe that the next logical step is a simple and cost-effective approach of allowing children with high threshold peanut allergy to ingest tolerated amounts of peanut. The approach is based in part on our prior success with allowing children to ingest milk and egg in tolerated forms, and the promise seen in OIT studies¹²⁻²⁰.

Currently, allergists perform OFCs in the office setting by feeding supermarket forms of peanut measured with simple kitchen materials often using foods brought in by the patient. We propose that allowing children with high threshold peanut allergy to ingest tolerated, sub-threshold amounts of peanut, using home-purchased, home-measured foods based on the results of an OFC, may be associated with benefits such as further increased threshold with time and potentially sustained unresponsiveness (SU, remission off daily ingestion), should be safe, and result in improved quality of life. This approach may become a prototype for studying additional foods. Additionally, we will undertake immunologic genomic, and transcriptomic characterization of a high threshold endotype of peanut allergy to inform identification of biomarkers and mechanisms of threshold, response to therapy, reaction severity, and SU/tolerance/remission.

Therefore, we have designed a trial to determine if there is a benefit to allowing children with high threshold peanut allergy to ingest home measured amounts of peanut below their threshold, as compared to standard care avoidance. This document serves as the SAP for the CAFETERIA trial.

2. STUDY OBJECTIVES

2.1 Primary Clinical Objective

The primary objective of this study is to determine whether allowing ingestion of subthreshold amounts of peanut in those with a high threshold (tolerate at \geq 143 mg peanut protein but <5043 mg peanut protein on supervised double-blind, placebo-controlled oral food challenge [DBPCFC]) will be associated with attaining even higher thresholds over time compared to those avoiding peanut.

2.2 Secondary Clinical Objectives

The secondary clinical objectives include assessing the development of sustained unresponsiveness (a surrogate term for tolerance without daily ingestion), effects on quality of life, changes in skin prick test mean wheal diameter and safety in participants randomized to peanut ingestion compared to avoidance.

3. STUDY OVERVIEW

3.1 Study Design

This is a prospective two-arm, parallel-group, randomized (1:1) controlled open trial of a diet allowing ingestion of tolerated, home-purchased, home-measurable quantities of peanut in children allergic to peanut in higher amounts.

3.1.1 Study Duration and Time Points

Participants in the intervention group may begin with different starting amounts of peanut butter, depending upon the baseline reaction threshold (Figure 1). Every 8 weeks, participants will return for attempting to ingest a higher amount of peanut along a ladder of 1/8 tsp, ¹/₄ tsp, 3/8 tsp, ¹/₂ tsp, ³/₄ tsp, 1 tsp, 1.5 tsp, 2 tsp, 3 tsp. A repeat DBPCFC (desensitization DBPCFC visit; primary endpoint visit) will be performed 8 weeks after reaching 1 tablespoon (or equivalent peanut product after exceeding 3/8 teaspoon; see Protocol Section 3.1.3), or at 72 weeks. Subjects tolerating the full challenge amount will add peanut to the diet for 16 weeks and then avoid peanut for 8 weeks, followed by a DBPCFC to assess for sustained unresponsiveness.

Participants in the control arm will receive monthly telephone follow up. They will have a visit 16 weeks following the baseline DBPCFC for review of avoidance instructions and collection of a blood sample, saliva and stool for mechanistic studies, and quality of life and diet questionnaires. They will have a repeat DBPCFC (desensitization DBPCFC visit; primary endpoint visit) to peanut at a time determined by a surveillance algorithm (see Protocol Section 13.3) to ensure similar lengths of time between initial and repeat DBPCFC between the two randomization groups. In brief, after the baseline DBPCFC, patients in the avoider group will be assigned a 'time to the second DBPCFC' as a value randomly selected from the distribution of the consumer patients with the same baseline reactive dose. Initial distributions for time to DBPCFC will be assumed to follow a uniform distribution centered on the treatment expectations anticipated by the clinicians based on initial DBPCFC (i.e. ~32 weeks for those who fail at 3000 mg, ~72 weeks for those who fail at 300 mg) plus minus 3 weeks. After the recruitment of every 10 patients, the time to OFC distribution for each baseline reactive dose will be updated as a uniform distribution derived from the time to OFC of consumer patients if 2 or more

observations are available, otherwise we will keep the initial uniform distribution for that baseline reactive dose.

Figure 1: Study Scheme

3.1.2 Randomization and Masking

Children age 4-14 years with high threshold peanut allergy will be randomly assigned (1:1) to ingest a sub-threshold amount of peanut daily or to follow avoidance. Randomization will be stratified by age ($4 - \langle 10 \rangle$ years of age vs. 10 - 14 years of age) and cumulative reaction dose at baseline DBPCFC (443mg; 1043 mg; 2043 mg; 5043 mg). The data and statistical coordinating center (DSCC) will maintain control of stratification and randomization. Randomization will be performed centrally through a Web-based data collection system that automates the delivery of the randomization assignments. Neither the participant nor the investigators will be blinded to randomization assignment. The study staff conducting the DBPCFCs, however, will be blinded to the participant randomization status. Trial oversight will be provided by an independent Data and Safety Monitoring Board (DSMB).

4. ANALYSIS POPULATIONS

Four populations will be used for all summaries and analyses.

Screened Population

The screened population will consist of all subjects who signed a consent form and met enrollment eligibility prior to the baseline DBPCFC.

Intent-to-Treat (ITT) Population

The ITT population will consist of all randomized subjects grouped by their assignment at randomization whether or not they actually received the treatment to which they were assigned. This sample will be used for summaries and analyses of the primary and secondary (where applicable) clinical endpoints. The ITT population will be used for the primary and secondary (where applicable) analyses and description of patient and baseline characteristics.

All Available Data Population

The All Available Data population will consist of randomized subjects with at least one longitudinal assessment of the secondary clinical endpoint (e.g., Quality of Life). Subjects will be analyzed in the group they were randomized. The All Available Data population will be identical to the ITT population if all randomized subjects have at least one measurement.

Per Protocol Population

The Per Protocol Population will consist of subjects in the intervention group who attended two-thirds of the updosing visits and the desensitization DBPCFC visit and subjects in the control group who did not consume peanut based on IgG 4 levels.

Safety Population

The Safety population will consist of all randomized subjects in the intervention group who received any amount of peanut after the baseline DBPCFC and all randomized subjects in the control group. The Safety population will be identical to the ITT population if all randomized subjects in the intervention group receive the assigned treatment. The Safety population will be used for the analysis of safety data.

5. STUDY ENDPOINTS

5.1 Primary Clinical Endpoint

The primary endpoint is success on the desensitization DBPCFC defined as the ability tolerate a dose at least 2 steps higher than the baseline DBPCFC or 9043 mg of peanut protein.

5.2 Secondary Clinical Endpoints

The following secondary clinical endpoints will be assessed:

- 1. Sustained unresponsiveness (intervention group) or natural tolerance (control group; attaining tolerance without an intervention)
- 2. Safety parameters (acute allergic reactions, including anaphylaxis, gastrointestinal side effects)
- 3. Quality of life measures
- 4. Skin prick test mean wheal size

5.3 Exploratory Clinical Endpoint

1. Severity Score for acute allergic reactions

6. STATISTICAL METHODOLOGY

6.1 General Principles

Continuous variables will be summarized using the following descriptive statistics: number of non-missing values, means, standard deviations, medians, interquartile range, maximum, and minimum. Categorical variables will be summarized using number of non-missing values, counts and percentages.

For any variable measured at multiple points in time, change from baseline will be calculated as the difference between the value of the variable at a specific point in time (e.g. 1 year) minus the baseline value. Relative change from baseline will be calculated as the value of a parameter at a specific point in time minus the baseline value of the parameter divided by the baseline value of the parameter. Percent change will be calculated as the relative change multiplied by 100.

All hypothesis testing will be conducted at the 0.05 two-sided significance level unless otherwise specified. P-values will be rounded to three decimal places. P-values less than 0.001 will be reported as <0.001 in tables. P-values greater than 0.999 will be reported as >0.999.

Should any of the statistical methods proposed prove unsuitable during data analysis, more appropriate methods will be used. These include data transformation (for example to a logarithmic scale) to satisfy model assumptions such as normally distributed residuals with constant variance, the application of non-parametric techniques or the use of a different link function or modeling technique.

Additional ad-hoc analyses may be conducted as deemed appropriate.

All analyses will be conducted using SAS V9.4 or higher and R statistical software (version 4.2.2 or higher).

6.2 Missing Data

6.2.1 Missing Baseline Data

Missing baseline values will not be imputed and summaries will be based on all available data.

6.2.2 Missing Primary Outcome Data

The handling of missing outcome values in the primary endpoint is described in section 6.5.1.2.

6.2.3 Missing Secondary Clinical Outcomes Data

The handling of missing outcome values in the secondary clinical endpoints is described in section 6.5.2.

6.3 Crossover

Crossovers are subjects who after randomization switch from the allocated treatment to the non-allocated treatment. Subjects randomized to peanut ingestion who never consume peanut after the baseline DBPCFC or who permanently discontinue peanut consumption will be considered crossovers. In addition, subjects randomized to avoidance who start ingesting peanut and continue consumption through the desensitization DBPCFC visit (or study discontinuation, whichever comes first) will be considered to have crossed over. Should crossover occur, crossovers will be analyzed as belonging to the group to which they were randomized according to the ITT principle in all efficacy analyses. Safety analyses will be conducted according to the definition of the Safety population described in section 4.

6.4 Patient Characteristics

6.4.1 Patient Disposition

Disposition will be summarized in the screened and ITT populations.

Disposition summaries of the screened population will include:

- The number of consented subjects eligible for the baseline DBPCFC
- The number and percentage of consented subjects who were not randomized and reasons (e.g., subject ingested <143 mg peanut protein; subject ingested ≥5043 mg peanut protein; subject did not complete baseline food challenge visit)
- The number and percentage of consented subjects randomized

Disposition in the ITT population will be summarized by randomization group and will include:

- The number of subjects randomized
- The number and percentage of subjects who received their assigned procedure
- The number and percentage of subjects withdrawn or lost to follow-up by the desensitization DBPCFC visit (primary endpoint visit) and the primary reason for withdrawals
- The number and percentage of subjects withdrawn or lost to follow-up by the sustained unresponsiveness visit in the intervention group and the primary reason for withdrawals

6.4.2 Patient Characteristics

6.4.2.1 Demographic characteristics

Demographics including age, sex, race and ethnicity will be summarized by randomization assignment using the appropriate descriptive statistics.

6.4.2.2 Baseline characteristics

Baseline characteristics will be summarized by randomization assignment using the appropriate descriptive statistics. The specific baseline variables collected are detailed in the protocol and include baseline cumulative reaction dose (443 mg; 1043 mg; 2043 mg;

5043 mg), medical/allergy history, physical exam findings, vital signs, spirometry, skin prick test to peanut blood samples, quality of life survey, diet questionnaire, urine pregnancy if child bearing potential, and saliva and stool collection.

6.5 Primary and Secondary Clinical Endpoint Analyses

6.5.1 Analysis of the Primary Clinical Endpoint and Determination of Sample Size

6.5.1.1 Determination of Sample Size

For sample size calculations, we assume a conservative estimate for the proportion of spontaneous tolerance in the control group of 10%. We believe that an additional absolute increase of 45 percentage points under the intervention is feasible and clinically meaningful (55% vs. 10%). We also assume a drop-in rate (avoiders to consumers) and drop-out rate (consumers discontinuing study treatment) of 5% and 20%, respectively. This results in an attenuated effect size of 33.75% percentage points (46% vs. 12.25%. A total of 72 children randomized with equal probability to the active or control arm (36 per group) provides approximately 85% power to detect a difference of 33.75% (46% versus 12.25%) in the proportion of children who tolerate at least 2 steps higher amount from baseline or the full amount of peanut protein by the desensitization DBPCFC visit, based on a 0.05 level continuity corrected chi-squared test. We believe the drop-in rate will be kept at a minimum since parents and children will likely not attempt dose escalation on their own. Peanut-specific IgG levels will be monitored in all participants and those with rising peanut-specific IgG from ingestion could be identified. The drop-out rate is conservative, based on our prior experience, which reported a drop-out rate of 15%.

6.5.1.2 Analysis of Primary Clinical Endpoint

The primary clinical endpoint of this study is the ability to tolerate a dose at least 2 steps higher than the one tolerated at baseline or 9043 mg of peanut protein by the desensitization DBPCFC. The null hypothesis is that there is no difference in the probability of participants who can consume higher amounts of peanut between subjects randomized to ingestion compared to subjects randomized to avoidance. The proportion of subjects in the intervention and the control group meeting the primary outcome will be compared using a continuity corrected chi-squared test at the 0.05 significance level.

As the intent-to-treat principle includes all randomized subjects in the primary analysis, patients who are missing the trial's primary endpoint will have their outcome imputed using multiple imputation assuming that the data are missing at random (MAR). The imputation model will be stratified by randomization assignment and include age, sex, baseline reactive dose strata, clinical severity during baseline DBPCFC as well as peanut-specific IgE levels (log transformed) at baseline and week 16. Since the model includes a mixture of variables types (i.e. continuous and discrete), a fully conditional specification method will be used.²¹ The imputation process will be repeated 30 times to achieve maximal stability of

the procedure. A separate analysis will be conducted for each completed-andimputed dataset. Rubin's rule²² will be used to combine the 30 analyses and test the difference in success rates between the intervention and control groups.

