### 13.3 Measures to Minimize Bias

Although this is an open trial, DBPCFCs will be performed by staff blinded to randomization assignment. Randomization will be stratified by age (4-<10 years vs. 10-14 years) and reaction dose at the initial DBPCFC, balanced by blocks of 4 and 6. This will guarantee that both treatment arms have similar distribution of those covariates without pre-specifying a number of patients per strata, which will limit enrollment. Clinical samples for mechanistic studies will be received by the laboratory personnel in coded fashion without indication of intervention allocation.

Defining the timing for the DBPCFC in the control group: Time from randomization to the DBPCFC will be dictated by the achievement of 1 tbsp threshold in children in the intervention group. In order to ensure that the two trial arms will have the same time to DBPCFC on average, we will develop an adaptive algorithm to assign a time to DBPCFC in avoiders that matches that of the consumers. After the baseline DBPCFC, patients in the avoider group will be assigned a 'time to the second DBPCFC' as a value randomly selected from the distribution of the consumer patients with the same baseline reactive dose. Initial distributions for time to DBPCFC will be assumed to follow a uniform distribution centered on the treatment expectations anticipated by the clinicians based on initial DBPCFC (i.e. ~32 weeks for those who fail at 3000 mg, ~72 weeks for those who fail at 300 mg) plus minus 3 weeks. After the recruitment of every 10 patients, the time to OFC distribution for each baseline reactive dose will be updated as a uniform distribution derived from the time to OFC of consumer patients if 2 or more observations are available, otherwise we will keep the initial uniform distribution for that baseline reactive dose. The statistician will receive an email from RedCap alerting them that 10 new patients had been accrued; and will update the timing distributions. Once a patient is randomized to the Avoider group, the unblinded statistician will send the timing of the second DBPCFC to the study coordinator, who will enter the assigned time into RedCap. For monitoring and data checking purposes, the unblinded statistician will maintain their own records. Inconsistencies will be identified and resolved in a timely manner within the monitoring process when producing data inconsistencies and data completeness reports.

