### 13.4.2 Primary Analysis of Primary Endpoint(s)/Outcome(s)

The primary endpoint of this study is the ability to tolerate a dose at least 2 steps higher than the one tolerated at baseline or 9043 mg of peanut protein by the desensitization DBPCFC. The proportion of subjects in the intervention and the control group meeting the primary outcome will be compared using a continuity corrected chi-squared test at the 0.05 significance level. As the intent-to-treat principle includes all randomized subjects in the primary analysis, patients who are missing the trial's primary endpoint will have their outcome imputed using multiple imputation techniques. Missing data in the primary endpoint will be assumed to depend only on the observed values, i.e., data are missing at random (MAR). Data imputation under this assumption will be performed using the proposed multiple imputation method by Rubin. Covariates in the imputation model will include treatment assignment, gender, age and baseline reactive dose strata, clinical severity during DBPCFC as well as peanut-specific IgE levels at baseline and week 16.

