### **13.4.3** Supportive Analyses of the Primary Endpoint(s)/Outcome(s)

Sensitivity analyses will be performed to assess the sensitivity of the primary analysis results to choice of statistical test and missing imputation procedure as well as departures of the MAR assumption and to treatment cross-overs. Sensitivity analysis include:

a) Stratified Chi-square test (by baseline reactive dose and age strata)

b) Fisher's exact test under 5 ad-hoc imputation strategies: i) all are failures, ii) are all failures except the highest dose at baseline which are successes, iii) all are failures except highest two doses at baseline, iv) all are successes except lowest dose at baseline, and v) all are successes. That is, the first and last of the five are the least conservative, respectively, and the others are in between but use the baseline dose as a means of an intermediate approach, which also incorporates a possible difference in distribution of baseline doses between the groups.

c) If the MAR assumption is not tenable, statistical methods that assume missing not at random (MNAR) such as pattern mixture models for non-ignorable missing data will be considered.

d) When cross-over rates are high, the ITT effect of being assigned to treatment may differ from the effect of actually receiving treatment. As a sensitivity analysis, we will perform an instrumental variable (IV) analysis to obtain an unbiased estimate of the treatment effect, using randomization assignment as the instrument.

e) Given the potential impact of COVID-19 pandemic on subject's return for the Desensitization DBPCFC visit, we will perform a sensitivity analysis that examines the effect of intervention on primary endpoint success adjusting for time from randomization to Desensitization DBPCFC visit and whether patients were randomized prior to study pause in March 2020 using logistic regression modelling.

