# **13.7** Sample Size Considerations

The primary objective of this study is to compare the proportion of children who at the desensitization DBPCFC tolerate an amount at least 2 steps higher than the baseline amount or who tolerate the full dose (9043 mg) of peanut protein between the active and the control arm in the HT group. Secondary clinical outcomes of this study include sustained unresponsiveness, skin prick test mean wheal diameters, quality of life, and adverse events. For sample size calculations, we assume a conservative estimate for the proportion of spontaneous tolerance in the control group of 10%. We believe that an additional absolute increase of 45 percentage points under the intervention is feasible and clinically meaningful (55% vs. 10%). We also assume a drop-in rate (avoiders to consumers) and drop-out rate (consumers discontinuing study treatment) of 5% and 20%, respectively. This results in an attenuated effect size of 33.75% percentage points (46% vs. 12.25%). A total of 72 children randomized with equal probability to the active or control arm (36per group) provides approximately 85% power to detect a difference of 33.75% (46% versus 12.25%) in the proportion of children who tolerate at least 2 steps higher amount from baseline or the full amount of peanut protein by the desensitization DBPCFC, based on a 0.05 level continuity corrected chi-squared test. We believe the dropin rate will be kept at a minimum since parents and children will likely not attempt dose escalation on their own. The drop-out rate is conservative, based on our prior experience, which reported a drop-out rate of 15%.

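### With complete data, the continuity correction in the primary test gives up about 4 to 5 points of power that an uncorrected stratified (CMH) test would keep at close to 5% type I error; with missing outcomes the comparison turns on an unstated pooling rule

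*SAP*

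**What the plan says.** Protocol 13.4.2 and SAP 6.5.1.2 set the same primary analysis: the proportions of children "meeting the primary outcome will be compared using a continuity corrected chi-squared test at the 0.05 significance level", with no stratification. The sample size uses that test too. The plan "provides approximately 85% power to detect a difference of 33.75% (46% versus 12.25"%), "based on a 0.05 level continuity corrected chi-squared test" (SAP 6.5.1.1, Protocol 13.7), with 36 children per arm.

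The allocation is stratified. Protocol 13.3 states: "Randomization will be stratified by age (4-<10 years vs. 10-14 years) and reaction dose at the initial DBPCFC", in blocks of 4 and 6. SAP 3.1.2 gives four dose levels: "cumulative reaction dose at baseline DBPCFC (443mg; 1043 mg; 2043 mg; 5043 mg"). With two age groups that makes 8 strata.

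A stratified test is planned only as sensitivity analysis (a) in Protocol 13.4.3 and SAP 6.5.1.3: "Stratified Chi-square test (by baseline reactive dose and age strata"). Neither document says whether it carries a continuity correction.

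Missing primary outcomes are multiply imputed 30 times. SAP 6.5.1.2 says Rubin's rule "will be used to combine the 30 analyses and test the difference in success rates between the intervention and control groups", but does not say which estimate and which variance are combined.

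**The concern.** The nominal two-sided level is 5%, but a continuity-corrected test with 36 per arm rejects far less often than that under the null. The unused error rate is lost power, and the documents give no reason for accepting the loss or for leaving the randomisation strata out of the primary test. The number of children is fixed and withdrawals are not replaced (Protocol 11.3), so the choice of test is one of the few things that can still affect power.

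The loss matters more if the true effect is smaller than planned. It can also decide a result near the boundary: against 4/36 successes in the control arm, 11/36 in the intervention arm is not significant with the correction and is significant without it.

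**Working it through.** **Inputs.** Two-sided 0.05 (SAP 6.1); 55% v 10% before attenuation, drop-out 20%, drop-in 5%, 36 per arm (SAP 6.5.1.1); 2 age by 4 dose strata, blocks of 4 and 6 (Protocol 13.3, SAP 3.1.2). The documents do not give stratum shares, how prognostic the strata are, or a missing-outcome rate. These are assumed and varied.

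**1. The plan's own figures.** Attenuated rates:
- intervention: 0.80 × 0.55 + 0.20 × 0.10 = 0.46
- control: 0.95 × 0.10 + 0.05 × 0.55 = 0.1225
- difference d = 0.3375

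Fleiss formula with correction: n = (n′/4)[1 + √(1 + 4/(n′d))]². Setting n = 36 gives n′ = 30.3. With mean rate 0.29125,

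power = Φ{[d√n′ − 1.96√(2 × 0.29125 × 0.70875)] / √(0.46 × 0.54 + 0.1225 × 0.8775)} = Φ{(1.858 − 1.259)/0.597} = 84.2%.

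Using 36 in place of n′ (no correction) gives Φ{(2.025 − 1.259)/0.597} = 90.0%. Enumerating all 37 × 37 tables gives 85.9% for the corrected test. The stated 85% is right.

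**2. Exact behaviour of the unstratified tests, 36 v 36.**

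| Test | Power, 46% v 12.25% | Type I error at 10% | at 12.25% | at 29% |
|---|---|---|---|---|
| Corrected (planned) | 85.9% | 1.4% | 1.8% | 2.8% |
| Uncorrected | 90.9% | 5.8% | 5.6% | 5.2% |

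The corrected test's maximum over all null rates is 2.8%. The correction costs 90.9 − 85.9 = 5.0 points here, but dropping it without stratifying overshoots 5%.

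**3. A boundary case.** For 11/36 v 4/36, |ad − bc| = |11 × 32 − 25 × 4| = 252 and the denominator is 36 × 36 × 15 × 57 = 1,108,080.
- Corrected: 72 × (252 − 36)²/1,108,080 = 3.03, p = 0.082
- Uncorrected: 72 × 252²/1,108,080 = 4.13, p = 0.042

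The corrected test needs 12/36: 72 × (288 − 36)²/(36 × 36 × 16 × 56) = 3.94, above 3.84.

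**4. Stratified test, simulated.** In each stratum with N children, n₁ and n₀ per arm and T successes, E = n₁T/N and V = n₁n₀T(N − T)/[N²(N − 1)]. The CMH statistic is [Σ(O − E)]²/ΣV. Over 8 strata with equal dose shares, a 60/40 age split, no prognostic effect and 20,000 trials per scenario:

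| Test | Power | Type I error at 12.25% |
|---|---|---|
| Corrected, unstratified | 85.5% | 1.7% |
| Uncorrected, unstratified | 90.6% | 5.1% |
| CMH, uncorrected | 90.3% | 4.8% |
| CMH, corrected | 84.1% | 1.7% |

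Arm sizes vary here, so the uncorrected unstratified figure is below the exact 5.6% at 36 v 36. With skewed stratum mixes, uncorrected CMH has power 89.5–90.0% and type I error 4.5–5.2%. In the most extreme mix tried (70% of children in one dose level), a separate run gave 89.8% against 85.7% for the planned test, and 83.5% for CMH with the correction kept. If the strata are prognostic (assumed), uncorrected CMH reaches about 91–94%.

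**5. Equivalents.** The corrected test reaches 89.6% at 40 per arm and 90.6% at 41, so matching CMH takes about 82 − 72 = 10 more children. At 40% v 12.25%, power is 70.9% (corrected) v 78.5% (CMH); at 35% v 12.25%, 53.2% v 63.4%.

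**6. Missing outcomes.** Assumed missing completely at random, 30 imputations, imputation models simpler than the SAP's.

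| Missing (assumed) | Pooled CMH score: power (type I error) | Pooled Wald difference: power |
|---|---|---|
| 5% | 87.8% (4.1%) | 89.6% |
| 10% | 86.1% (2.7%) | 88.1% |
| 20% | 81.1% (2.2%) | 83.3% |

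A second simulation, with a simpler by-arm imputation, pooled the corrected chi-squared statistics directly (the D2 rule). Power was 83.8%, 81.8% and 77.1%, against 88.1%, 85.9% and 81.6% for pooled CMH, whose type I error was 4.4%, 4.4% and 3.8%. If the SAP means D2 pooling, CMH gains about 4 points. If it means a pooled Wald difference, CMH loses about 2. That Wald test is slightly liberal with complete data, however: its exact type I error is 5.7% at 12.25%.

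**The case against.** The strongest reply is that nothing here is an error. The trial was sized on the corrected test and will be analysed with it, the stated power is right, and a conservative test is a conventional choice at 36 per arm. All of that stands; the point is efficiency.

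A second reply is that the primary analysis is multiple imputation, so a complete-data comparison may not describe it. That also stands. The gain cannot be asserted for the analysis as written, because the SAP leaves the pooling open.

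A third is that replacing the primary test late, in a trial where investigators know the allocation, with one that rejects more readily invites doubt. Protocol 13.3 also has an unblinded statistician who updates control timing from the intervention arm's progress. The SAP's opening statement permits revisions before data lock, but permission does not remove the doubt. It has to be met by how the change is made.

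A reader might also infer that sensitivity analysis (a) already supplies the extra power. The documents do not support this: they do not say that test is uncorrected, and with the correction kept, stratification gives only about 83–84% when the strata are not prognostic.

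**Conclusion.** The planned test is valid but conservative. With complete data at 46% v 12.25%, an uncorrected CMH test over the 8 randomisation strata gives about 90% power against 85–86%, a gain of about 4–5 points, with type I error close to 5% for null rates of 10% and above (about 3% at a null rate of 5%). This held over every stratum mix tried and needs no prognostic effect. Removing the correction supplies the gain. Stratification holds the error rate, and adds power only if dose or age is prognostic, which the documents do not establish.

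Three stronger readings should be resisted. The 85% is not miscalculated. The primary test does not inflate error. And the 4–5 points at about 5% error cannot be carried over to the imputed analysis: there the pooled CMH score is conservative, and whether it beats the planned analysis depends on a pooling rule that SAP 6.5.1.2 does not give. The missing-data figures also rest on assumed missing rates and simplified imputation models.

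The unstated pooled quantity is a gap in its own right: if any primary outcome is missing, the primary p-value is not fully determined by the text.

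**What to change.** Before data lock, amend SAP 6.5.1.2–6.5.1.3 and Protocol 13.4.2–13.4.3 as follows.

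- Make the CMH test, stratified by baseline reactive dose and age as randomised and stated explicitly to be without continuity correction, the primary test.
- Report the unstratified corrected chi-squared test beside it as a sensitivity analysis.
- Name what Rubin's rule combines. One option is the CMH score Σ(O − E) with its null variance ΣV; note that it is conservative when outcomes are missing.
- Record the reason for the change. It should be decided by people without sight of outcomes by arm, which rules out the unblinded statistician described in Protocol 13.3.
- Keep the 85% in Protocol 13.7 and SAP 6.5.1.1, with a note that it is a conservative figure based on the corrected test.

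If the sponsor prefers to keep the corrected test, one sentence should still name the estimate and variance to be pooled, since the corrected chi-squared statistic supplies neither directly.

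The cost is text in two sections of each document, plus notes to the sample-size sections. No children or data are added: age and dose are already collected and are in the imputation model. The real downside is the appearance of a late move to a test that rejects more readily, which is why the recorded reason and the side-by-side report are part of the change.
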